### **4.3. Inclusion Criteria**

To be eligible for inclusion into the study, the subject should meet the following criteria:

- On follow up at SGH between the ages of 21 and 75 years old who had received or are

- scheduled to receive a living donor renal transplant between January 2016 to January 2023
- Has to receive tacrolimus (FK) (Prograf®; Astellas Pharma, Singapore), mycophenolic acid (MPA) (Cellcept®; Roche, Basel, Switzerland or Myfortic®; Novartis Pharma AG, Basel, Switzerland) and prednisolone as triple immunosuppressive drug maintenance regimen

#### 4.4. Exclusion Criteria

A subject will be excluded from the study if any of the following criteria are met:

- Planned to be initiated on non-standard doses of tacrolimus (e.g. planned to initiate on sub-therapeutic doses of tacrolimus)
- Evidence of active liver disease or gastrointestinal disorder that might interfere with the ability to absorb oral medication
- Contraindications to tacrolimus (FK) – e.g. hypersensitivity
- Takes concurrent medications which are known to severely interact with FK (e.g. verapamil, azoles, rifampicin, erythromycin or clarithromycin)

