There has been increasing evidence to suggest the implementation of pre-transplantation genotyping to guide the initial FK dose to achieve target FK concentrations as quickly as possible (Chen SY et al, 2013; Shuker N et al, 2016; Pallen N et al, 2016; Zhang J et al. 2010). Min SI et al revealed that in RTx patients who received equal doses of FK, the CYP3A5 expressers (\*1\*1 and \*1\*3 genotypes) had lower FK level and a higher incidence of acute cellular mediated rejection than the CYP3A5 non-expressers (CYP35 \*3\*3 genotype). Furthermore, multivariate analysis identified CYP3A5 expression as an independent risk factor for cellular mediated rejection (odds ratio 2.79; p=0.043) (Min SI et al, 2010). On the contrary, there are a few studies that report contradictory results of genotype-guided FK dosing as being useful in attainment of target therapeutic levels. A randomized controlled trial by Thervet et al demonstrated that while target FK levels were achieved earlier in incident kidney transplant recipients whose tacrolimus dose was chosen based on CYP3A5 genotype versus a control group that started tacrolimus based on standard weight-based dosing (Thervet et al, 2010), no

differences were seen in patient survival, nephrotoxicity, or acute rejection over the three-month follow-up. A key limitation of the study was tacrolimus was introduced only 7 days after transplantation in the CYP3A5 genotype-based dosing group while it was started at time of transplantation in the weight-based dosing group. Prevalence of CYP3A5 genotypes is also different in various ethnicities. For example, the Caucasian proportions of CYP3A5 expressers (CYP3A5 \*1\*1 and \*1\*3) were 18% while in our local multiethnic population, CYP3A5 expressers make up 51% of the renal transplant population (Loh PT et al, 2008).

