#### Treatment/dosing:

The standard arm will comprise of historical controls who are patients who had received renal transplant from a living donor and followed up at SGH between January 2016 - December 2020 and received standard weight-based dosing of tacrolimus.

The intervention genotyping arm will comprise of patients who are scheduled to receive renal transplant from a living donor between January 2021 to January 2023. They will be assigned to receive the initial CYP3A5 genotype-based tacrolimus (FK) dose as determined by their CYP3A5 genotype:

| Likely phenotype                               | Diploypes | Initial Prograf ® dosing
(mg/kg/day given in 2 divided doses) |
|--|-----------|---|
| Extensive metabolizer
(CYP3A5 expresser)    | CYP3A*1*1 | 0.20  |
| Intermediate metabolizer
(CYP3A5 expresser) | CYP3A*1*3 |   |
| Poor metabolizer
(CYP3A5 non-expresser)     | CYP3A*3*3 | 0.15  |

The FK dose will be rounded off to the nearest 0.5 mg. FK will be administered at 8 am and 8 pm on an empty stomach.

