#### Rationale for Selection of Dose:

Patients will be assigned to receive an initial CYP3A5 genotype-based tacrolimus (FK) dose of

0.15 mg/kg/day (CYP3A5 non-expresser) or 0.20 mg/kg/day (CYP3A5 expresser).

The current Clinical Pharmacogenetics Implementation Consortium (CPIC) Guidelines for CYP3A5 genotype and Tacrolimus Dosing recommend that

- CYP3A5 expressers e.g. carriers of at least one CYP3A5\*1 allele) receive 1.5 – 2 times the standard starting dose of tacrolimus
- CYP3A5 non-expressers e.g. carriers of CYP3A5 \*3/\*3 receive 0.075 mg/kg/dose twice daily

At SGH, the standard starting dose of Prograf® is 0.15 mg/kg/day. Based on the CPIC guidelines, CYP3A5 expressers will receive an initial dose of 0.20 mg/kg/day (rounded down). Subsequent drug doses will be adjusted based on drug levels.

All the proposed initial doses of tacrolimus are within the local approved package insert for Prograf®, which recommends an initial dose of 0.15 to 0.30 mg/kg/day for adult kidney transplant patients.

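### The non-standard-dose exclusion has no numeric meaning, and for historical controls it is applied to a planned dose, retrospectively and unmasked, when the primary-endpoint troughs are very probably already charted

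*Protocol*

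**What the plan says.** - **Exclusion (section 4.4).** A single list serves both cohorts. It excludes patients "Planned to be initiated on non-standard doses of tacrolimus (e.g. planned to initiate on sub-therapeutic doses of tacrolimus". The only guide to the meaning of *non-standard* is that example; no mg/kg bound is given.
- **Standard dose (section 5, Rationale for Selection of Dose).** "At SGH, the standard starting dose of Prograf® is 0.15 mg/kg/day". The same paragraph says "CYP3A5 expressers will receive an initial dose of 0.20 mg/kg/day", and the dose table under Treatment/dosing agrees. It adds that all proposed doses lie within the package insert, which "recommends an initial dose of 0.15 to 0.30 mg/kg/day for adult kidney transplant patients".
- **Control arm (section 5, Treatment/dosing).** Controls are 2016-2020 living-donor recipients who "received standard weight-based dosing of tacrolimus". No mg/kg value or tolerance is attached.
- **Screening (section 4.2).** Investigators screen the controls after transplant, among patients still followed up. Prospective patients are screened while their transplant is being planned.
- **Masking and outcome (section 5).** The study is open-label. The primary endpoint is the proportion with a tacrolimus trough in range at day 3 and at day 7, and Clinical assessment lists troughs among the laboratory data for days 0 through 7.

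**The concern.** The criterion has two weaknesses. The first is a matter of wording. *Non-standard* is undefined, and the one dose the protocol calls the site's standard differs from the dose it assigns to expressers.

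The second matters more. For a control, the transplant, the first dose and the early troughs all lie in the past. Section 4.4 nevertheless asks what was *planned*, while Treatment/dosing asks what was *received*. Where the two are unclear or disagree, an investigator with the chart open can keep the patient as weight-based or remove the patient as planned non-standard. Nothing stops that decision from being made with the day-3 level in view. The genotype arm is not exposed in this way, because its patients are screened before any trough exists. Any resulting bias falls on one side of the primary comparison.

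**Working it through.** The protocol gives no on-target rate, effect size or split of its 100 subjects, so there is no stated figure to reproduce. The check compares the passages and then adds an illustration.

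**1. Readings of *standard*.** The expresser dose relative to the stated standard is 0.20 / 0.15 = 1.33.

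| Reading | Expressers in the genotype arm | Controls |
|---|---|---|
| Standard means 0.15 mg/kg/day | Excluded on the literal wording | Bounded, but no tolerance given |
| Standard means the insert range, 0.15 to 0.30 | Not excluded | A control started at 0.20 passes section 4.4 |
| Only sub-therapeutic starts are excluded, as in the example | Not excluded | No upper bound |

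The readings that keep expressers in also loosen the rule for controls. Treatment/dosing does not settle this, because it uses the word *standard* without a number.

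**2. What is known at screening.**

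| | Genotype arm | Controls |
|---|---|---|
| Time of screening | Before transplant | After transplant |
| First dose | Not yet given | In the past |
| Day-3 and day-7 troughs | Do not exist | Very probably charted |
| Masking of the screener | None described; no outcome to mask | None described |

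The charting entry is an inference from section 4.2 and from Endpoints and Clinical assessment in section 5. The protocol does not state it as a fact.

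**3. Size of a possible effect (assumed inputs).** Let p be the true on-target rate among controls and f the share of off-target controls dropped. The observed rate is p / [p + (1 - p)(1 - f)].

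| p | f = 5% | f = 10% | f = 20% |
|---|---|---|---|
| 30% | 31.1% (+1.1 points) | 32.3% (+2.3) | 34.9% (+4.9) |
| 40% | 41.2% (+1.2) | 42.6% (+2.6) | 45.5% (+5.5) |
| 50% | 51.3% (+1.3) | 52.6% (+2.6) | 55.6% (+5.6) |

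For example, with p = 40% and f = 10%: 0.40 / (0.40 + 0.60 × 0.90) = 0.40 / 0.94 = 42.6%. With an assumed 50 controls, that is three charts: 20/50 = 40% becomes 20/47 = 42.6%.

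If on-target controls were dropped instead, the rate would fall. With p = 50% and f = 20%: 0.40 / (0.40 + 0.50) = 44.4%, or 5.6 points lower. The documents do not indicate which direction is likelier.

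**4. Whether a dose tolerance is workable.** Treatment/dosing rounds to the nearest 0.5 mg. If that applies to each of two daily doses, and was also the practice for controls (both assumed), the daily dose moves by at most 2 × 0.25 = 0.5 mg. At an assumed 50 to 80 kg this is 0.5/50 = 0.010 down to 0.5/80 = 0.006 mg/kg/day. The gap between the two protocol doses is 0.20 - 0.15 = 0.05, so rounding alone would not blur them.

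**The case against.** **On the wording.** A reader might infer that section 4.4 contradicts the dose table and removes every expresser, about half of the genotype arm given that "CYP3A5 expressers make up 51% of the renal transplant population". The documents do not support that. The criterion's own example is sub-therapeutic dosing, both assigned doses lie within the cited insert range, and the higher dose is the intervention itself. In addition, section 5 takes genotyping blood from study participants, so expresser status would normally be unknown when eligibility is screened. This objection stands. What remains is an undefined term that clashes with the dose rationale only when read literally.

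**On the controls.** A reader might infer that control membership rests wholly on an unrecorded intention. That is also too strong. Section 5 separately defines controls by the dosing they received, and charts may hold a first dose or a documented plan. But the protocol does not require either to be used, gives no mg/kg window, and does not say which of *planned* and *received* governs.

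**On generality.** Retrospective screening exposes every criterion in a declared open-label pilot with historical controls. That is true. This criterion is more exposed than most because it concerns starting dose, which bears directly on the trough, and because it asks about intent.

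**On size.** A reader might take 50 controls with 20 in range, remove 10 low-dose starters who are all out of range, and report a rise from 40% to 20/40 = 50%. That case needs a third of the off-target controls (10/30) to go. Moreover, removing genuine low-dose starters is what the criterion is meant to do, so the shift would not measure outcome-driven selection.

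**Conclusion.** The point holds as a selection problem in the control cohort, together with a smaller matter of undefined wording. The criterion has no numeric meaning, is applied retrospectively and unmasked, and refers to a planned dose although the arm is defined by dosing received. The control on-target rate can therefore depend on knowledge of the outcome.

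The direction is unknown. The shift of about 1 to 6 points is an illustration that rests on an assumed on-target rate of 30-50% and an assumed 5-20% of off-target controls dropped. It is not an estimate of what will happen, and it presumes that troughs are charted when controls are screened. Pilot status does not remove the concern, because section 8.1 intends the findings to inform a larger study. The criterion should be amended. Nothing here bears on which starting dose is right.

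**What to change.** 1. **Reconcile the wording.** Make section 4.4 consistent with the dose rationale and table in section 5, for example by stating that a protocol-assigned genotype dose does not count as non-standard.
2. **Controls: use recorded data.** Replace *planned* with the recorded first-day dose and weight, judged against a written definition of the standard weight-based dosing in force at the site when each control was transplanted, with a pre-set tolerance. The 0.15 mg/kg/day figure is stated in the present tense, and no section says it applied throughout 2016-2020. Using it untested could remove controls dosed correctly for their time.
3. **Fix the order.** Abstract dose and weight first, settle and lock eligibility, and only then abstract trough levels.
4. **Report.** Give the number of controls excluded on this ground, with reasons.

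The cost is one amendment and a fixed order of chart abstraction, with no new patients or procedures. The small downside is that some controls may be lost if recorded practice departed from the written definition.

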### 5. STUDY DESIGN AND PROCEDURES/METHODOLOGY

#### Methodology

This is a prospective, investigator-initiated, open-label single center pilot study conducted at the Singapore General Hospital (SGH). It will compare selected end-points between a historical control group (which was dosed by mg/kg) and a prospective intervention group (which will be dosed according to genotype).

#### Treatment/dosing:

The standard arm will comprise of historical controls who are patients who had received renal transplant from a living donor and followed up at SGH between January 2016 - December 2020 and received standard weight-based dosing of tacrolimus.

The intervention genotyping arm will comprise of patients who are scheduled to receive renal transplant from a living donor between January 2021 to January 2023. They will be assigned to receive the initial CYP3A5 genotype-based tacrolimus (FK) dose as determined by their CYP3A5 genotype:

| Likely phenotype                               | Diploypes | Initial Prograf ® dosing
(mg/kg/day given in 2 divided doses) |
|--|-----------|---|
| Extensive metabolizer
(CYP3A5 expresser)    | CYP3A*1*1 | 0.20  |
| Intermediate metabolizer
(CYP3A5 expresser) | CYP3A*1*3 |   |
| Poor metabolizer
(CYP3A5 non-expresser)     | CYP3A*3*3 | 0.15  |

The FK dose will be rounded off to the nearest 0.5 mg. FK will be administered at 8 am and 8 pm on an empty stomach.

#### Rationale for Selection of Dose:

Patients will be assigned to receive an initial CYP3A5 genotype-based tacrolimus (FK) dose of

0.15 mg/kg/day (CYP3A5 non-expresser) or 0.20 mg/kg/day (CYP3A5 expresser).

The current Clinical Pharmacogenetics Implementation Consortium (CPIC) Guidelines for CYP3A5 genotype and Tacrolimus Dosing recommend that

- CYP3A5 expressers e.g. carriers of at least one CYP3A5\*1 allele) receive 1.5 – 2 times the standard starting dose of tacrolimus
- CYP3A5 non-expressers e.g. carriers of CYP3A5 \*3/\*3 receive 0.075 mg/kg/dose twice daily

At SGH, the standard starting dose of Prograf® is 0.15 mg/kg/day. Based on the CPIC guidelines, CYP3A5 expressers will receive an initial dose of 0.20 mg/kg/day (rounded down). Subsequent drug doses will be adjusted based on drug levels.

All the proposed initial doses of tacrolimus are within the local approved package insert for Prograf®, which recommends an initial dose of 0.15 to 0.30 mg/kg/day for adult kidney transplant patients.

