Given the differences in CYP3A5 genotype prevalence among races and the controversy in clinical benefits of such a pro-active dosage strategy, the impact of CYP3A5 genotype-guided dosing on clinical outcome remains to be answered, especially in the local multi-ethnic population. This pro-active approach may also sound promising for the local multi-ethnic population where majority of the renal transplant population are CYP3A5 expressers who may require a higher initial dose of FK based on genotyping profile (Loh PT et al, 2008). Faster achievement of target concentrations could potentially reduce the risk of graft rejection because of underexposure and toxicity because of overexposure (Birdwell KA et al, 2015). A recent meta-analysis including 21 studies evaluating the effect of CYP3A5 polymorphism on kidney transplant recipients concluded that there is a significantly increased risk for transplant rejection for those with the CYP3A5\*1\*1 or CYP3A5\*1\*3 genotype (P=0.04; odds ratio=1.32) (Rojas et al, 2015). Furthermore, patients with the CYP3A5\*3\*3 (nonexpresser) genotype exhibited dose-adjusted trough concentrations 1.8–2.5 times higher than CYP3A5 expressers during the first year after transplantation (Rojas et al, 2015).

This study aims to shed light on the possible impact of CYP3A genotype-based FK dosing on FK target achievement and clinical outcome after RTx in a multi-ethnic population where current evidence is lacking. This data would be helpful to the physicians so that by knowing the genotype of the patient before undergoing transplantation, they would be able to decide on the starting dose of FK so as to avoid low trough levels and risk of acute rejection or high trough levels and risk of nephrotoxicity.

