### **6.3. Safety Monitoring Plan**

The data and safety monitoring will be performed by the Principal Investigator (PI) and a team of Co-Investigators. The patient will be reviewed daily when hospitalized and will then be followed up at outpatient as per current standard of care. Data will be reviewed by the PI on a three-monthly basis and it will be stored in an encrypted device. Study will be stopped if more than 25% of the patients in the genotyping arm have a tacrolimus trough of < 3 ng/mL or > 20 ng/mL on day 3

As an additional safety precaution, the tacrolimus drug levels achieved with current protocol and the starting dose of tacrolimus will be reviewed after every 10 participants recruited. The starting dose will not deviate from the dosage recommended in the drug insert.

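### The expresser starting dose is said to rest on a guideline of 1.5 to 2 times the standard dose, but it is 1.33 times the standard, below the cited range, and no reason is given

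*Protocol*

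**What the plan says.** All the relevant statements stand in Section 5 of the protocol, mostly under Rationale for Selection of Dose.

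- The guideline as cited: expressers "receive 1.5 – 2 times the standard starting dose of tacrolimus", and non-expressers "receive 0.075 mg/kg/dose twice daily".
- The reference dose: "At SGH, the standard starting dose of Prograf® is 0.15 mg/kg/day".
- The dose chosen and its basis: "Based on the CPIC guidelines, CYP3A5 expressers will receive an initial dose of 0.20 mg/kg/day (rounded down".
- The doses by genotype: "0.15 mg/kg/day (CYP3A5 non-expresser) or 0.20 mg/kg/day (CYP3A5 expresser". The table under Treatment/dosing gives the same two figures, so 0.20 is not a typing slip in one place.
- The label, which "recommends an initial dose of 0.15 to 0.30 mg/kg/day for adult kidney transplant patients".

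The comparison group is a historical cohort that received standard weight-based dosing (Sections 4.1 and 5). Sections 4.1 and 8.1 describe the study as a pilot whose findings may lead to a larger, adequately powered and probably multi-centre trial.

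**The concern.** A reader who takes the rationale at its word will describe the intervention as dosing at the guideline multiple. The protocol's own figures say otherwise: the dose lies below the lowest multiple the guideline is said to recommend.

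This bears on what the trial can conclude. Non-expressers in the intervention arm start on the site standard, so the expresser step is the only place where the planned starting dose differs from that of the controls. If that step is smaller than the cited one, the trial gives evidence on the smaller step only. The stated purpose is to decide whether a larger trial is worth designing, so the decision should rest on a correct description of what was given.

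**Working it through.** **Inputs, all from the protocol.** Standard starting dose 0.15 mg/kg/day; cited expresser multiple 1.5 to 2; expresser dose 0.20 mg/kg/day; cited non-expresser dose 0.075 mg/kg twice daily; label range 0.15 to 0.30 mg/kg/day (all from Rationale for Selection of Dose). Share of expressers in the local transplant population 51% (Section 1).

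**Step 1: try to reproduce the stated dose.** Cited multiple × standard dose:
- lower end: 1.5 × 0.15 = 0.225 mg/kg/day
- upper end: 2 × 0.15 = 0.30 mg/kg/day

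The stated 0.20 is not in this range.

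**Step 2: the multiple actually used.** 0.20 / 0.15 = 1.33.
- Shortfall from the lower end: 1 − 0.20/0.225 = 11%
- Shortfall from the upper end: 1 − 0.20/0.30 = 33%
- The increase over standard is 33%, against 50% to 100% as cited. That is two thirds of the smallest cited increase and one third of the largest.

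**Step 3: does anything in the text account for the gap?**
- *Rounding down.* Taking 0.225 down to the next step of 0.05 does give 0.20. This shows where the figure probably came from, but the result falls outside the cited range.
- *The rule of rounding to the nearest 0.5 mg.* This concerns the dose administered. At assumed weights of 50, 60, 70 and 80 kg the daily doses at 0.15 are 7.5, 9, 10.5 and 12 mg, and at 0.20 they are 10, 12, 14 and 16 mg. The ratio is 1.33 each time.
- *The label.* The range 0.15 to 0.30 contains 0.20, but it also contains all of 0.225 to 0.30, so it does not force the lower figure.
- *A different reference dose.* The cited non-expresser dose is 2 × 0.075 = 0.15 mg/kg/day, equal to the site standard. Using it as the reference changes nothing.

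**Step 4: size of the contrast in the arm as a whole.** Non-expressers change by 0.15/0.15 − 1 = 0%. Assuming that 51% of those enrolled are expressers, and that the controls started on the stated site standard, the average planned increase in starting dose is:
- as planned: 0.51 × 0.333 = 17%
- at the cited multiples: 0.51 × 0.5 = 25.5% to 0.51 × 1 = 51%

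**The case against.** The strongest reply is that nothing is hidden. The multiple, the standard, the dose and the fact of rounding down are printed within a few lines, a dose can be based on a guideline without equalling it, and rounding 0.225 down to a 0.05 step does give 0.20. This stands as far as it goes: the rounding is disclosed. What is not disclosed is that it takes the dose below the cited range, or why. The rationale offers no other basis for the expresser multiple.

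The second reply is that this is a pilot without a power calculation, whose hypothesis concerns genotype-based dosing in general. A null result would be inconclusive at any multiple. That is also fair. It limits the consequence but does not correct the description of the intervention.

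Three stronger readings are tempting, and the documents do not support them.

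- A reader might infer that a null result *will* be misread as evidence against the guideline. No section says the results will be presented that way, and the doses are openly stated. All that follows is that such a reading would be unsupported.
- A reader might infer that the step is too small to bring expressers into the target range, because Section 1 cites non-expressers as having "dose-adjusted trough concentrations 1.8–2.5 times higher than CYP3A5 expressers". If trough is proportional to dose, a 1.33-fold step leaves expressers at 1.33/2.5 = 53% to 1.33/1.8 = 74% of non-expresser troughs. But that ratio is reported for the first year, whereas the target of 10 to 15 ng/mL applies to week 1. The cited 1.5 multiple also corrects only in part (1.5/2.5 = 60% to 1.5/1.8 = 83%). The protocol gives no trough variability from which to compute in-range proportions. Whether the dose is adequate is a clinical question and not part of this point.
- A reader might see a second contradiction in Section 6.3, which provides for review of the starting dose after every 10 participants and adds: "The starting dose will not deviate from the dosage recommended in the drug insert". A review within the label range does not say that the doses in Section 5 will change, so it does not contradict them.

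**Conclusion.** The point holds as an internal contradiction between a stated basis and a stated figure. The cited guideline and the stated standard give 0.225 to 0.30 mg/kg/day. The protocol gives 0.20, which is 1.33 times the standard and 11% below the lower end. This result uses the protocol's own numbers and needs no assumption.

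The consequence is one of interpretation. The expresser step is the only planned *starting-dose* contrast with the controls, taking their standard weight-based dosing to be the 0.15 mg/kg/day that the protocol gives as the site standard. It is not the only difference between the groups: the controls come from an earlier period, two induction agents are allowed, and the target range is specified for the genotyping arm. Whatever the trial shows, it bears on a 1.33-fold step. A weak or null result could not be read as evidence about the cited 1.5- to 2-fold adjustment. The arm-average figures (17% against 25.5% to 51%) also rest on the 51% share of expressers applying to those enrolled.

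**What to change.** Reconcile three things in Section 5, across Treatment/dosing and Rationale for Selection of Dose: the cited multiple, the claim that the dose is based on it, and the dose itself. Which of them changes is for the sponsor and clinicians, and this review proposes no dose.

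If the dose stands:
- state the actual multiple, 1.33 times the standard, in the rationale;
- remove the claim that the dose follows the 1.5 to 2 times recommendation, or qualify it by saying that the dose lies below that range and why;
- limit the conclusions, including the decision on a larger trial, to the 1.33-fold step tested.

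In that case the cost is a few sentences, with no change to the analysis or the sample size. The stated justification becomes less favourable, because the trial can no longer be presented as applying the guideline multiple.
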